8.6.2. CT Scan Protocol

Patient enrollment into this study is based on the independent physician review and assessment of Core Lab produced three-dimensional reconstructions of high resolution, contrast-enhanced spiral CT scans. To ensure consistency, below are the requirements for acquisition of the CT Scan:

- Only high resolution, contrast-enhanced spiral CT scans are acceptable.
- Data must be uncompressed.
- Preferred maximum slice spacing is 1mm. *In no case should it exceed 2mm.*
- The preferred protocol, shown below, is easier to attain with a multi-row scanner. If the preferred protocol cannot be used, an alternate protocol is provided.
- Instruct patient not to move during scan. Do not move table height, position, or field of view during scan. If such movement occurs, repeat scan in its entirety.
- Send data to the core lab identified in §2 via CD or per Core Lab instructions. Questions can also be forwarded to the Core Lab directly as identified in §2.

Parameter	Preferred	Alternate
Scan Mode	Helical/Spiral	
Scan Parameters	140kVp, Auto mA, 0.5sec	140kVp, 280mA (min), 1.0sec
Collimation	0.625 to 1mm	2mm
Slice Spacing	0.625 to 1mm	2mm
Superior Extent	Thoracic aorta, at least 5cm above celiac artery origin	
Inferior Extent	Lesser trochanter of femur	
Patient Instruction	Single breath hold	1 st hold: 5cm above celiac to bifurcation 2 nd hold: bifurcation to lesser trochanter
Contrast	Standard non-ionic	
Volume and Rate	150mL at 3 to 4 mL/sec	
Scan Delay	ROI - threshold 90Hu in aorta	ROI - threshold 90Hu in aorta or 25sec delay
Field of View	Large body	
Window Level	400/40	

8.6.3. Screening and Baseline Evaluations

Following informed consent, the patient is to be pre-screened for eligibility by the investigator. Any information provided by the patient's referring physician or from the patient's chart will be recorded on the relevant CRF. If any of this information is inadequate, procedures may be repeated / performed by the investigator to verify eligibility.

The following steps must be completed within three months prior to enrollment into the study unless otherwise indicated. All such steps that are not performed within three months of enrollment into the study must be repeated prior to the procedure.

- [a] Assess eligibility criteria.
 - [b] Perform a physical examination, including patient height and weight, vital signs, and ASA Class determination.
 - [c] Review the patient's medical history.
 - [d] Perform blood lab analyses including serum creatinine, blood urea nitrogen, hematocrit, and hemoglobin.
 - [e] Perform an ankle-brachial index assessment bilaterally.
- Note: The ABI test may be performed after initial screening but prior to the procedure if more convenient for the institution. ABIs may be done in the office (vascular lab is not required.)
- [f] Perform diagnostic imaging per institutional standard of care.
 - [g] Collect a baseline high resolution, contrast-enhanced CT scan per the protocol in §8.6.2. Follow the preferred protocol to the extent possible.
 - [h] Document the patient's relevant concomitant medications (cardiac/circulatory medications).

Fax the SCREENING FORM as requested in [a] through [g] to the Endologix Clinical Department at [contact].

The investigator is to proceed with enrollment of the patient and procedure scheduling **ONLY after receiving written documentation from the Sponsor** that the patient meets the respective enrollment criteria, and is confirmed to meet all other inclusion and exclusion criteria. **The Sponsor will clearly CONFIRM the patient for enrollment in the ELIGIBILITY Form faxed or e-mailed to the investigator.** The investigator will sign the bottom of the CRF in the space provided to acknowledge receipt of the fax.

Any patient who is determined to be a screen failure must have clear documentation of the reason(s) for failure in the CRFs. **In such cases, the Sponsor will clearly DENY the patient for enrollment in the ELIGIBILITY Form to the investigator.** The investigator will sign the bottom of the CRF in the space provided to acknowledge receipt of the fax.

8.6.4. Enrollment

The investigator and the Sponsor will assure all **SCREENING AND BASELINE** CRFs are complete with no unresolved issues.

Only after the Sponsor notifies the investigator of the patient eligibility by fax with a **CONFIRM** designation is the patient to be scheduled for the procedure.

The date of study enrollment is the date that the procedure is performed, as documented on the **PROCEDURE REPORT** CRF. This date is also considered Day 0 for follow-up date calculation.

8.6.5. Procedural

Prepare the patient for the procedure according to §7.4 and institutional protocols. Follow the Instructions for Use to select and prepare the bifurcated device, the Fenestrated Stent Graft device, the Renal Stent Grafts, and other ancillary devices for use.

- [a] Introduce the bifurcated delivery system into the designated (ipsilateral) femoral artery. Refer to the corresponding Instructions for Use for all details related to placement of the bifurcated device.
- [b] Deliver and deploy the bifurcated stent graft at the target location. Refer to the corresponding Instructions for Use to prepare and deliver any accessory stent grafts as needed.
- [c] Introduce the Fenestrated stent graft delivery system into the designated (ipsilateral) femoral artery.

Refer to the Fenestrated Stent Graft System Instructions for Use for all details related to placement of the device, introduction and deployment of renal stent grafts through the indwelling guide sheaths, deployment of the fenestrated stent graft, and delivery system removal.

- [d] Document at the time (in 24 hour clock format) that the following procedural steps were completed.
- first breakage of skin
 - bifurcated delivery system sheath entry
 - bifurcated delivery system sheath removal
 - fenestrated delivery system sheath entry
 - cannulation of the renal arteries
 - renal stent graft implant completion
 - fenestrated stent graft deployment/implant
 - renal stent graft flaring
 - fenestrated delivery system sheath removal
 - skin closure
- [e] Complete the immediate post-implant evaluation section on the **PROCEDURE REPORT** Form. Fax the form to the Endologix Clinical Department at [contact]
- [f] Report any events that occurred during the procedure or recovery on the **ADVERSE EVENT** CRF. If an event is a serious adverse event, provide the additional event details on the **Serious Adverse Event** section of the CRF. See §8.7 for adverse event reporting requirements.
- [g] A copy of the operative report is requested.
- [h] A copy of the intraoperative angiography run is requested. This may be burned to CD and shipped to Endologix Clinical Research Department.

8.6.6. Pre-Discharge

Before the patient is discharged from the hospital the following steps are completed.

- [a] Record the patient's weight and vital signs.
- [b] Obtain a blood sample for serum creatinine, blood urea nitrogen, hematocrit, and hemoglobin measurements.
- [c] Perform Ankle-Brachial Index testing bilaterally.
- [d] Perform a physical examination.
- [e] Perform other tests or imaging per institutional standard of care.
- [f] Document any new or discontinued medications (cardiac/circulatory).
- [g] A copy of the hospital discharge report or note is requested.

- [h] Report any adverse finding from the diagnostic testing, or specific events that occurred since the procedure. If an event is a serious adverse event, provide the additional event details on the **Serious Adverse Event** section of the CRF. See §8.7 for adverse event reporting requirements
- [i] The hospital staff should complete the *Patient Implant Card* (provided in the stent graft product packaging) and give it to the patient so that he or she can carry it at all times. The patient should be instructed to refer to the card anytime he or she visits a health practitioner, particularly for any additional diagnostic procedures (e.g., MRI).

8.6.7. Post-Discharge Follow-up Visits

The patient post-discharge follow-up visits are to occur post-procedurally at **30±14 days** (one month visit), **180±30 days** (six month visit), **365±60 days** (one year visit), **730±90 days** (two year visit), **1095±90 days** (three year visit), **1460±90 days** (four year visit), and **1825±90 days** (five year visit).

- [a] Obtain a blood sample for serum creatinine, blood urea nitrogen, hematocrit, and hemoglobin measurements.
- [b] Perform a physical exam.
- [c] Perform Ankle-Brachial Index testing bilaterally.
- [d] Diagnostic Imaging:
 - **CT Scan:** When a CT Scan is performed, collect it as a high resolution, contrast-enhanced CT scan using the same acquisition parameters required by the Core Lab as for the baseline exam. Forward the CT Scan to the Core Lab identified in §2.2. A copy of the site diagnostic report is requested.
 - As per institutional standard of care, record any other imaging performed and provide a copy of the diagnostic report[s].
- [e] Document any new or discontinued medications (cardiac/circulatory).
- [f] Report any adverse finding from the diagnostic testing, or events that occurred since hospital discharge. If an event is a serious adverse event, provide the additional event details on the **Serious Adverse Event** section of the CRF. See §8.7 for adverse event reporting requirements.

8.6.8. Missed Patient Visits

The Investigator(s) will make every attempt to follow the patients enrolled in the study.

If a patient cannot be reached for a follow-up visit, the Investigator will document on the CRF, the efforts undertaken to contact the patient or the patient's primary health care provider. These efforts should include 2 attempts of telephone contact at separate dates and times, and a registered letter before the end of the follow-up window. If a patient cannot be reached for the follow-up visit and misses the scheduled visit, the visit will be recorded as a missed visit on the date of last attempted contact. Patients who miss a visit will not be considered withdrawn. At the next visit interval, the Investigator and/or designee will attempt to contact the patient again for follow-up. Should this attempt to contact the patient fail, a family member should be contacted in addition to the patient. Patients who miss 2 sequential follow-up visits will be considered lost to follow-up at the second missed visit and exempt from further study follow-up. After the patient is exited from the study, the Investigator will attempt to determine if the patient is alive, including searching national mortality registries as permitted by local laws.

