4.3. TRIAL DESIGN

This is a multicenter, prospective, single arm clinical trial. Patients with JAA/PAA who are suitable candidates for endovascular repair using the Endologix Fenestrated Stent Graft System will be considered for enrollment.

After this protocol and the patient informed consent form are reviewed and approved by the local Ethics Committee or responsible Institutional Review Board, potential patients will be offered participation in the study. This will be accomplished through the patient's reading of the informed consent form in the patient's native language and discussion of the study with the patient by the investigator and site personnel. Agreement to participate and to attend all follow-up visits will be documented with the patient's signature on the informed consent form, with appropriate signatures of the site investigator and an impartial witness.

After providing written informed consent, screening and eligibility determinations will be performed. Patients will undergo a high resolution, contrast-enhanced computed tomography angiography (CT) scan of the relevant aortic and aortoiliac vasculature within three months of the scheduled procedure. Evaluation of the aortic and vascular anatomy suitability per this protocol, as depicted on the CT scan, will be performed by the site investigator and by an independent core laboratory. Other tests include a physical examination, review of patient medical history for exclusionary conditions, selected blood chemistry and hematology analyses, and ankle-brachial index determination.

Upon acceptance for enrollment, patients will be scheduled for the endovascular repair procedure.

Note: An investigational site may not enroll more than 20% of the total Trial Phase enrollment.

Following patient discharge from the hospital, the first follow-up visit will be made at one month (± 2 weeks). A CT scan will be performed to assess aneurysm morphology and device integrity and patency, as well as the status of the renal arteries and implanted stent grafts. Subsequent follow-up will be made at six months, one year, and annually to five years.

Continued patient follow-up beyond five years is outside of the scope of this study. Nonetheless, all patients should be monitored and evaluated per the institutional standards of care for patients who receive an endovascular stent graft.

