8.3. METHOD FOR ASSIGNMENT TO TREATMENT GROUP

Eligible patients will be assigned a patient number to be used in all documentation. The patient identification number will use the following convention:

XXX-YYY-ZZZ

Where:

XXX is the designated site three-digit ID number assigned by Endologix.

YYY is a three digit sequential patient ID number beginning with 301.

ZZZ is the first letter of the patient’s first, middle, and last name. For patients with the same initials at a site, the letter ‘X’ will be used as the middle initial for the second patient. For patients without a middle name, ‘---’ will be used for the middle initial.

Upon satisfactory completion of all site start-up training and documentation requirements, Endologix will supply the site with written ‘Go’ notification that initiation of patient screening for study enrollment is authorized.

A Screening Log will be maintained by the site to document each patient who undergoes the screening process and the final determination of eligibility.

The actual procedure date will serve as the “start” date from which follow-up evaluations will be measured. After treatment, each patient will be evaluated prior to hospital discharge and will then be evaluated at one month (defined as 30 ± 14 days), at six months (defined as 180 ± 30 days), and at annual follow-ups at 1 year (defined as 365 ± 60 days), and at 2 to 5 years (± 90 days).

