8.6.9. Study Patient Exit

Study patients exit the study when no additional follow-up visits, procedures, or data collection are required. A Study Exit Form must be completed and full source documentation present for the reason(s). A subject may be exited from the study in the following instances:

- Patient signs a consent, surgery is scheduled, but the device is not implanted
- Patient withdraws from the study
- Patient is lost-to-follow-up
- Patient death
- Patient completes all study follow-up

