9. RISK ANALYSIS

The decision to repair an aortic aneurysm is generally based on the risk of rupture, the risk of complications of surgery, and patient preference. There are currently two methods used to repair aortic aneurysms. The most common and conventional method is an open surgical repair, with the implantation of a synthetic graft to replace the diseased aneurysmal vessel through a large abdominal incision. Recent technological developments have resulted in an alternative, minimally invasive, endovascular aneurysm repair, in which a stent graft is placed within the aorta through a small incision in the groin. Blood can then flow through the stent graft and is excluded from the aneurysmal portion of the aorta.

The disadvantages of open surgical repair are: general anesthesia is required, it is a major abdominal surgery (large incision), has a significant surgical complication rate, and typically requires a long hospital stay and recovery. EVAR enables local or regional anesthesia to be used, uses a minimally invasive groin incision for catheter-based access, and has been reported in US clinical studies to offer a lower operative complication rate, reduced blood loss and procedure times, and shorter hospital stay. In contrast to open repair, EVAR is a relatively new treatment, long term results have not been fully established, and life-long surveillance is recommended to verify stent graft integrity and patency and continued aneurysm exclusion. Currently, five device systems are FDA-approved and marketed in the US for endovascular infrarenal abdominal aortic aneurysm repair. All of these devices require the introduction of catheter-based treatment devices varying in outer diameter profile from 20Fr to 25Fr (ipsilateral). Standard vascular exposure is indicated for access. Prospective clinical study results support the safety and effectiveness of these stent grafts through early follow-up (to 30 days) and in late follow-up to one year and to up to five years. These and other devices are CE Marked and are available in other international regions. One custom device is available in Europe for JAA endovascular repair; however, no ‘off-the-shelf’ endovascular devices are currently commercially available. No device is currently approved in the US for the endovascular repair of juxtarenal or pararenal aortic aneurysm.

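### The two-missed-visits rule can end follow-up before the one-year primary effectiveness visit, leaving some one-year outcomes missing that could at least partly be collected

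*Combined protocol and SAP*

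**What the plan says.** Section 8.6.8 treats one missed visit leniently: "Patients who miss a visit will not be considered withdrawn". The site must make two telephone attempts and send a registered letter. At the next interval it tries again, adding a family member if the patient still cannot be reached. After a second miss in a row the rule changes: "Patients who miss 2 sequential follow-up visits will be considered lost to follow-up at the second missed visit and exempt from further study follow-up". What is asked for after that is limited: "After the patient is exited from the study, the Investigator will attempt to determine if the patient is alive". Section 8.6.9 lists "Patient is lost-to-follow-up" among the reasons for which a patient may be exited.

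On timing, section 4.3 says: "Following patient discharge from the hospital, the first follow-up visit will be made at one month (± 2 weeks". Section 8.6.7 gives the windows as "30±14 days (one month visit), 180±30 days (six month visit), 365±60 days (one year visit". The pre-discharge assessment comes before these and is not a follow-up visit.

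Section 6.2 sets the primary effectiveness endpoint, Treatment Success, at one year. Section 10.2 expects about 15 patients without a one-year outcome and fills each by simple random (hot deck) sampling from patients with one-year outcomes. It adds sensitivity analyses: last observation carried forward, all missing as failures, all missing as successes, and a random draw against the performance goal. It also compares baseline characteristics of patients with and without missing data, and allows the worst score for a subgroup found not to be missing at random.

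**The concern.** A two-miss rule is usually harmless when many visits precede the primary assessment. Here only two do, so the rule can take effect before the primary time point. Nothing in 8.6.8, 8.6.9 or 10.2 exempts the one-year visit from it or asks for records, imaging or renewed contact to obtain the one-year outcome. The rule also counts missed visits. It is not limited to patients who proved unreachable at both.

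The hot deck then treats such a patient as resembling those who attended at one year. Someone who missed both early visits may differ, for example through illness or care elsewhere, and section 10.2 itself recognises that missing outcomes may go with failure. The stake is a small amount of avoidable missing data, and possible bias, in the primary effectiveness result.

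**Working it through.** **1. The plan's own figure.** Section 10.7.2 gives 82 evaluable patients, 80.58% power, null rate 0.80, alternative 0.90, one-sided alpha 0.05, and 15% drop-out.
- Exact binomial, n = 82: the smallest r with P(X ≥ r | 0.80) < 0.05 is r = 72, with P = 0.0458. Power is P(X ≥ 72 | 0.90) = 80.57%, which agrees.
- 82/0.85 = 96.5, rounded up to 97. The allowance is 97 − 82 = 15 patients.

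**2. Timing (section 8.6.7).**
- The six-month window closes on day 180 + 30 = 210.
- The one-year window opens on day 365 − 60 = 305 and closes on day 365 + 60 = 425.
- From day 210 to opening: 305 − 210 = 95 days. To closing: 425 − 210 = 215 days.

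**3. How many patients.** The documents give no per-visit miss rate. Assume independent misses with probability q at each of the first two visits, after the contact attempts have been made. The expected number exited before year 1 is 97 × q²:
- q = 0.10: 97 × 0.0100 = 1.0
- q = 0.15: 97 × 0.0225 = 2.2
- q = 0.20: 97 × 0.0400 = 3.9

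If misses cluster within patients, the number at a given q is higher.

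**4. Bound on the shift in the primary estimate.** Suppose patients with outcomes succeed at 0.90, so hot-deck values average 0.90. If every exited patient had in truth failed, the success rate is overstated by 0.90 × q² = 0.9, 2.0 or 3.6 percentage points. If every one had succeeded, it is understated by 0.10 × q² = 0.1, 0.2 or 0.4 points. The margin between the goal and the assumed rate is 10 points.

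**5. Effect on the planned missing-as-failure analysis.** With all 97 counted, 85 successes are needed (P = 0.0346). Take a true rate of 0.90 in those observed and no other missing data. Power by number missing is: 0, 83.0%; 1, 75.0%; 2, 64.9%; 3, 53.2%; 4, 40.8%. At the 15 missing that the plan expects, only 82 are observed and 85 cannot be reached, so recovering a few patients would not rescue that analysis.

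**6. What remains obtainable at one year.**
- Rupture, conversion and secondary intervention can be learned from the patient or from records, and Type I or III endoleak from a one-year CT. Under section 6.2 any one of these makes the patient a failure.
- Enlargement is measured against the initial post-operative scan (8.7.7), and migration against the position on the first post-operative scan (10.8.11). Section 8.4 schedules no CT before discharge, so a patient who missed both early visits normally has no reference scan unless one was taken elsewhere.
- Last observation carried forward may have no follow-up observation to carry forward for these patients.

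**The case against.** The strongest reply is that section 8.6.8 already works hard to keep patients. It requires documented calls, a registered letter and then family contact, and much of its text concerns patients who cannot be reached. Exempt and may be exited are permissive terms, and neither bars the use of data if a patient returns. About 15 missing outcomes are already allowed for, and section 10.2 includes missing-as-failure, all-success and worst-score analyses.

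Most of this stands and limits the point. It does not remove it. No further contact is required once the second visit is missed, so the one-year outcome is left to chance. The drop-out allowance protects power but not against bias, and the sensitivity analyses describe the uncertainty without recovering the outcome.

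Stronger readings are tempting, but the documents do not support them:
- A reader might infer that the full primary outcome could still be collected. Without a reference scan, some failures could be shown, but full success often could not be confirmed.
- A reader might infer that the rule favours the device. That is plausible, but nothing in the documents shows the direction.
- A reader might infer that a single patient decides the trial, since 72 of 82 passes (P = 0.0458) and 71 does not (P = 0.0836). That comparison is for 82 completers, whereas the primary analysis imputes to the whole treated population.
- A reader might carry the point to years 3 to 5, citing section 9: "life-long surveillance is recommended to verify stent graft integrity and patency and continued aneurysm exclusion". That sentence describes endovascular repair in general, leaving the study does not end clinical care, and the later evaluations are descriptive.

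**Conclusion.** The point holds for the one-year primary effectiveness endpoint. A patient who misses the one-month and six-month visits can leave the study 95 days before the one-year window opens, with only vital status sought afterwards. An outcome that could be at least partly established is then replaced by a draw from other patients.

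The size is probably small: about 1 to 4 of 97 patients, with an overstatement of the success rate of at most about 0.9 to 3.6 percentage points if all of them had failed. These figures rest on assumed independent miss rates of 10% to 20% per visit and a 90% success rate in observed patients. The true number is unknown. The wording of the rule is certain and its effect is not, so this is a cheap improvement in data completeness. The sample size calculation is unaffected.

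**What to change.** Amend section 8.6.8 so that missed visits alone do not make a treated patient lost to follow-up or exited before the one-year window closes on day 425. For the one-year visit, repeat the existing contact steps (two calls, registered letter, family or primary-care contact) whatever visits were missed earlier. Seek outside records or imaging that bear on the one-year outcome.

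Leave the other exit reasons in section 8.6.9 unchanged, including exit of consented patients whose device is not implanted, and leave the two-miss rule after year 1 as it is. The recruitment target of 97 and the planned analyses do not change. The cost is one paragraph of the protocol, a few more contact attempts, and a longer time formally on study for a few patients.
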